### **Risks of Research Procedures Performed on Subjects**

The risk of research procedures include psychological discomfort from participating in a clinical trial (less likely) and loss of confidentiality of medical records or economic data (rare).

Women of childbearing potential (able to get pregnant) must have a negative pregnancy test before being considered for the study. It is not known how apixaban could affect an unborn child. Women of childbearing potential must use an effective method of birth control while participating in this research, as directed by their physician.

### **Anticipated Risks of Drug**

Anticipated risks of apixaban are categorized as likely, less likely, and rare.

#### **Likely**

1. Anxiety related to participating in a clinical trial
2. Discomfort or bruising at sites for blood draws

#### **Less likely**

1. Major bleeding requiring transfusion of blood products
2. Clinically-relevant non-major bleeding
3. Nausea and vomiting

#### 4. Non-severe adverse drug reaction to apixaban

##### Rare

1. Severe allergic reaction (such as anaphylaxis) to apixaban
2. Thromboembolism
3. Fatal, life-threatening, or intracranial hemorrhage or stroke
4. Severe internal bleeding (such as gastrointestinal or retroperitoneal) that requires surgical or interventional laboratory intervention
5. Death
6. Other rare or unforeseen adverse effects

### **Protection of Subjects against the Risks of Research Procedures**

#### *Before Study Enrollment*

A rigorous screening process will be utilized to ensure that subjects with an increased risk of harm due to enrollment in the study are excluded from the study. This will include performing a detailed history and physical examination (to ensure that enrolled subjects truly fulfill all eligibility criteria) and carefully reviewing the results of laboratory testing (in particular, hematocrit, platelet count, INR, and serum creatinine).

#### *During Follow-Up*

Changes in health status during the 6-month follow-up period will be evaluated by the patient's primary physician, oncologist, and other routine providers. As apixaban is an FDA-approved drug commonly used for thromboprophylaxis and does not require routine follow-up clinical or laboratory monitoring for toxicity, the study will not mandate any follow-up visits or procedures other than those required for the patient's routine myeloma care.

#### *Protection against Loss of Confidentiality*

Subject confidentiality will be protected by maintaining all paper records in locked file cabinets in locked offices and all electronic records in password-protected computer files. All study data will be de-identified for storage in the electronic data repository. In addition, any identifying information will be removed from images or other data used in publication or presentations. All database information will be stored on computer systems that are located behind an electronic firewall, which will only permit access to certified study personnel. Access to study data files will be password-protected.

### **Ethical Considerations**

In this prospective, single-arm, single-center clinical study, we will be evaluating the impact of apixaban for primary prevention of VTE in patients with MM receiving IMiDs. The benefits of apixaban for primary prevention of VTE in patients with MM receiving IMiDs have not been assessed. The risk of bleeding in MM patients receiving apixaban has not been determined. Currently used thromboprophylactic regimens for primary prevention of VTE in MM patients receiving IMiDs largely consist of injectable anticoagulant regimens, such as enoxaparin and dalteparin. These regimens have not been well-evaluated for primary prevention of VTE in the MM population and are associated with patient discomfort, inconvenience, and limited medication adherence. Apixaban 2.5 mg orally twice daily has been shown to be safe and effective for prevention of VTE in a large general medical population. Therefore, a solid foundation for investigation of this thromboprophylactic regimen and equipoise for the proposed clinical trial exist. A successful trial has the potential to provide clinicians and patients with a more convenient, more comfortable, and potentially safer prophylactic regimen.

Because the proposed clinical trial involves a novel application of a U.S. FDA-approved anticoagulant, we will obtain written consent from all study subjects and Institutional Review Board approval at all study sites.

**Case Report Form**

Screening	
Inclusion criteria (all must be checked)	 Diagnosis of multiple myeloma  Receiving immunomodulatory therapy (either thalidomide [Thalomid], lenalidomide [Revlimid], and pomalidomide [Pomalyst])  18 years of age or older  Willing and able to provide written informed consent
Exclusion criteria (NONE must be checked)	 Pregnancy  Breastfeeding  Women of child-bearing potential who are unwilling or unable to use an acceptable method of birth control to avoid pregnancy for the entire study  Any prior venous thromboembolism  Contraindication to anticoagulant therapy  Conditions for which serious bleeding may occur including: 
 
○ Current or within last 6 months: intracranial bleeding, intraocular bleeding, gastrointestinal bleeding, endoscopically documented ulcer disease
 
○ Current or within last month: head trauma or other major trauma, major surgery
 
○ Current or within last 2 weeks: stroke, neurosurgical procedure
 
○ Current: gross hematuria, major unhealed wound, major surgery planned during the trial period, intracranial mass, vascular
 

	
malformation, or aneurysm, overt bleeding, blood dyscrasia
 
 Active and clinically significant liver disease
 
 Uncontrolled hypertension: systolic blood pressure >180 mm Hg or diastolic blood pressure >100 mm Hg
 
 Current endocarditis
 
 Requirement for ongoing anticoagulant therapy including mechanical heart valve replacement and atrial fibrillation
 
 Severe valvular heart disease, including rheumatic heart disease and mitral stenosis
 
 Bioprosthetic heart valve replacement
 
 Requirement for dual antiplatelet therapy or single agent antiplatelet therapy with clopidogrel, prasugrel, or ticagrelor
 
 Requirement for aspirin at a dose higher than 165 mg daily.
 
 Hemoglobin < 9 mg/dL
 
 Platelet count < 100,000/mm^3
 
 Calculated creatinine clearance (CrCl) < 25 ml/m
 
 Alanine aminotransferase or aspartate aminotransferase level > 2 times the upper limit of the normal
 
 Total bilirubin level > 1.5 times the upper limit of the normal
 
 Life expectancy < 12 months or hospice care
 
 Prisoners or subjects who are involuntarily incarcerated
 
 Subjects who are compulsorily detained for treatment of either a psychiatric or physical (eg, infectious disease) illness
 
 Receiving concurrent investigational agents or has received an investigational agent within the past 30 days prior to the first dose of study treatment (with the exception of approved medications being used for an approved indication, e.g., investigating a new dosing regimen for an approved indication).
 
 Any condition, which in the opinion of the investigator, would put the subject at an unacceptable risk from participating in the study
 
 Any other medical, social, logistical, or psychological reason, which in the opinion of the investigator, would preclude compliance with, or successful completion of, the study protocol


STOP HERE AND DO NOT ENROLL PATIENT IF ANY OF THE INCLUSION CRITERIA ARE ABSENT OR ANY EXCLUSION CRITERIA ARE PRESENT
	

Eligible
	
 Yes
 
 No

Written informed
	
 Yes

consent signed	 No
----------------	-----------------------------

Patient Demographics	
Study ID number	-----
Date of enrollment	____/____/____ MM DD YYYY
Date of birth	____/____/____ MM DD YYYY
Gender	 Male  Female
Ethnicity	 Hispanic/Latino  Non-Hispanic/Non-Latino
Race	 American Indian or Alaskan Native  Asian  White  Hispanic or Latino  Native Hawaiian or Pacific Islander  Black or African-American  Mixed race  Other, specify: _____
Weight (enter either weight and height OR BMI)	_____ (kg)
Height	_____ (cm)
BMI calculated	_____ (kg/m  )

Multiple Myeloma Characteristics	
Date of diagnosis	____/____/____ MM DD YYYY
Diagnosis status	 New diagnosis (diagnosis within the last 30 days)  Recurrent/relapsed disease
Diagnostic criteria	International Myeloma Working Group (IMWG) criteria  Must have at least one of the following:  Serum M-protein ≥ 0.5 g/dL by serum electrophoresis (SPEP) or for IgA myeloma, by quantitative IgA (>750 mg/dl)  Urinary M-protein excretion at least 200 mg/24 hours  Serum Free Light Chain (FLC) whereby the involved light chain measures ≥ 10 mg/dL and with an abnormal light chain ratio.
Stage	 R-ISS I – ISS stage I (B2M <3.5 mg/L and serum albumin ≥3.5 g/dL) and normal LDH and no del(17p), t(4;14), or

	
t(14;16) by FISH.   R-ISS II – Neither stage I nor stage III.   R-ISS III – ISS stage III (B2M ≥5.5 mg/L) plus LDH above normal limits and/or detection of one of the following by FISH: del(17p), t(4;14), or t(14;16).

Immunomodulatory therapy (check one)	
 thalidomide [Thalomid]   lenalinomide [Revlimid]   pomalidomide [Pomalyst]

Other therapies	
 proteasome inhibitors (PIs) (i.e., bortezomib [Velcade] and carfilzomib [Kyprolis])   corticosteroids (including dexamethasone)                  If yes, provide specific regimen (drug, dose, and frequency): _____   chemotherapy   hematopoietic cell transplantation   erythropoiesis stimulating agents   other

Comorbid Conditions	
Cardiovascular disease	
 Cardiomyopathy/diminished left ventricular systolic function                  If yes, EF (%) _____   Heart failure   Coronary artery disease                  If yes,                  CABG                   Coronary stent(s)                   Prior MI                   Unstable angina                   Stable angina    Rheumatic heart disease   Valvular heart disease   Atrial fibrillation or atrial flutter   Congenital cardiac abnormality   Pulmonary hypertension   Other structural cardiac disease

Valvular disease	
 Aortic Stenosis   Aortic regurgitation   Mitral regurgitation   Mitral Stenosis   Other
 
If yes,                  Any severe valve disease?

	 Yes  No
Hypertension	 Yes  No
Peripheral vascular/artery disease	 Yes  No
Carotid occlusive disease	 Yes  No
Cerebrovascular accident (strokes or TIAs)	 Yes  No
Family history of VTE	 Yes  No
History of bleeding	 Yes  No
Hypercholesterolemia	 Yes  No
Current alcohol consumption	 None  1-2 drinks per day  >2 drinks per day
Chronic liver disease (as noted in chart)	 Yes  No If yes, cirrhosis  yes  no
History of falls	 Yes  No
Cigarette smoking (check only 1)	 Current smoker  Former smoker  Never smoker
Major surgery within the past 3 months	 Yes  No If yes, date      MM      /      DD      /      YYYY  If within the last month, patient should not be enrolled.
Prior hospitalization within 30 days	 Yes  No
COPD	 Yes  No
Diabetes mellitus (Type I or II)	 Yes  No
Serum creatinine > 2.5 mg/dL	 Yes  No If yes, is patient on dialysis?  Yes

	
 No
 
If yes, patient should not be enrolled.
 
If no, creatinine clearance (Cockcroft-Gault) = ___ mg/dL

Concomitant medications	
 aspirin If yes, dose = ___ mg/daily
 
If > 165 mg/daily, patient should not be enrolled.
 
 daily NSAID use

Prior thromboprophylaxis regimen	
 Yes  No
 
If yes, check all that apply:
 
 LMWH  Fondaparinux  Unfractionated heparin  Warfarin  NOAC  Aspirin  Other: _____

Study Treatment	
Date study drug started	
___ / ___ / ___ MM DD YYYY

Date study drug stopped	
___ / ___ / ___ MM DD YYYY
 
Completed full 6 months of study drug?  Yes  No
 
If did not stay on drug for 6 months, reason why not?  Fulfilled criteria for a primary study outcome (VTE or major/clinically relevant non-major bleed)  Patient expired  Adverse drug event or side-effect  Change in clinical status (such as change in goals of care, comfort measures, hospice care)  Patient preference/withdrawal of consent


Superficial vein thrombosis
	
 Yes   No
 
If yes, date ____/____/____  MM DD YYYY

Other venous thrombosis (mesenteric, cerebral sinus, gonadal, etc.)
	
 Yes   No
 
If yes, date ____/____/____  MM DD YYYY

Pulmonary embolism
	
 Yes   No
 
If yes, date ____/____/____  MM DD YYYY
 
Confirmed by diagnostic imaging:   Yes   No  If yes, by?   CT   MRI   Pulmonary angiography   V/Q scan
 
Location:   Left   Right   Bilateral
 
RV dysfunction on echocardiogram or CT?   Yes   No
 
Associated with hemodynamic instability (syncope, shock, hypotension, cardiac arrest)?   Yes   No
 
Fatal?   Yes   No
 
Hospitalized?

	 Yes  No  Treatment:  Anticoagulation  Systemic fibrinolysis  Pharmacomechanical (catheter-based) therapy  Surgical embolectomy  IVC filter
Death	 Yes  No  If yes, date ____ / ____ / ____ MM    DD    YYYY  Cause of death:  PE  Myocardial infarction  Other cardiovascular  Cancer-related  Non-cardiovascular, non-cancer
Major or clinically relevant non-major bleed	 Yes  No  If yes, date ____ / ____ / ____ MM    DD    YYYY
Major bleed	 Yes  No  If yes, date ____ / ____ / ____ MM    DD    YYYY  Location:  Intracranial  Surgical/operative site  Gastrointestinal  Genitourinary  Retroperitoneal  Pericardial  Pulmonary  Other thoracic  Musculoskeletal  Nasopharyngeal

	
 Hematocrit or hemoglobin decrease without clear source   Other
 
Fatal?   Yes   No
 
Hospitalized?   Yes   No
 
Associated with hemodynamically instability?   Yes   No
 
Treatment:   Blood products   Surgery   Invasive procedure   Medical therapy (PCC, andexanet, etc.)

Clinically relevant non-major bleed
	
 Yes   No
 
If yes, date ____/____/____  MM DD YYYY
 
Location:   Intracranial   Surgical/operative site   Gastrointestinal   Genitourinary   Retroperitoneal   Pericardial   Pulmonary   Other thoracic   Musculoskeletal   Nasopharyngeal   Hematocrit or hemoglobin decrease without clear source   Other: _____
 
Hospitalized?   Yes   No
 
Treatment:

	 Blood products  Surgery  Invasive procedure  Medical therapy (PCC, andexanet, etc.)
Non-bleed adverse drug reaction	 Yes  No  If yes, date ____/____/____ MM    DD    YYYY  Type of reaction:  Anaphylaxis  Cutaneous (rash, etc.)  Liver function abnormalities  Other: _____  Hospitalized?  Yes  No  Study drug discontinuation?  Permanent stop  Temporary stop  Not discontinued
Myocardial infarction	 Yes  No  If yes, date ____/____/____ MM    DD    YYYY  Type:  ST elevation  Non-ST elevation  Fatal?  Yes  No  Treatment:  Systemic fibrinolysis  Percutaneous coronary intervention (angioplasty, stenting, etc.)  CABG  Medical management

Stroke/TIA	 Yes  No  If yes, date ____/____/____ 
MM    DD    YYYY
  TIA?  Yes  No  Stroke?  Yes  No  If yes, type of stroke:  Ischemic  Hemorrhagic  Other  Fatal stroke?  Yes  No  Treatment:  Systemic fibrinolysis  Percutaneous thrombectomy  Surgery  Other
------------	--

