### **Study Population**

Patients who are > 18 years of age or older with newly diagnosed MM, relapsed MM, MM on maintenance therapy and receiving IMiDs (i.e., thalidomide [Thalomid], lenalidomide [Revlimid], and pomalidomide [Pomalyst]).

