### **Study Inclusion Criteria**

- Men and women
- Age > 18 years
- Current or prior diagnosis of symptomatic MM based on International Myeloma Working Group (IMWG) guidelines (<http://imwg.myeloma.org/category/guidelines-2/>) and will be starting or already receiving IMiD therapy with thalidomide [Thalomid], lenalidomide [Revlimid], or pomalidomide [Pomalyst]
- IMiD therapy given in the setting of newly diagnosed MM, relapsed MM, progressive MM, maintenance therapy or consolidation therapy as per IMWG criteria

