### **Statistical Analysis Plan**

For this proof-of-concept study, we will calculate:

- 1) the 6-month rate of major and clinically relevant non-major bleeding
- 2) the 6-month rate of symptomatic VTE

We will also calculate 6-month rates of myocardial infarction and stroke.

The primary analysis will be intention-to-treat. Although study eligibility criteria warrant that the provider plans to treat the patient with IMiDs for at least 6 cycles, we will include any patient who has received at least 2 cycles in a modified intention-to-treat analysis.

Means, medians, and frequency distributions will be calculated for continuous variables. Number and percentages will be reported for binary and categorical variables. Differences between subgroups of interest will be examined using the chi-square or Fisher's exact test for binary and categorical variables and t-test or Wilcoxon Rank Sum for continuous variables (if the subgroups are of sufficient size for statistical comparison). Potential subgroup analysis will include patients newly diagnosed vs. recurrent/relapsed disease and concomitant medications (dexamethasone, etc.).

All tests will be two tailed and a p-value of <0.05 assumed to represent statistical significance. All analyses will be performed using SAS software.

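### The two-option disease-status field on the CRF leaves some eligible patients with no true answer, so the planned newly diagnosed versus relapsed subgroup cannot be built correctly from the form

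*Combined protocol and SAP*

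**What the plan says.** **Who may enter.** The Study Inclusion Criteria list five settings: "IMiD therapy given in the setting of newly diagnosed MM, relapsed MM, progressive MM, maintenance therapy or consolidation therapy as per IMWG criteria". They accept a patient who "will be starting or already receiving IMiD therapy" and give no maximum time since diagnosis. The Study Population section names maintenance separately from new and relapsed disease: "newly diagnosed MM, relapsed MM, MM on maintenance therapy and receiving IMiDs".

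**What the form records.** Under Multiple Myeloma Characteristics, the Diagnosis status field offers "New diagnosis (diagnosis within the last 30 days") and "Recurrent/relapsed disease". It has no box for maintenance, consolidation, progressive disease or other.

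**What the analysis uses.** The Statistical Analysis Plan states: "Potential subgroup analysis will include patients newly diagnosed vs. recurrent/relapsed disease". It defines neither term. Comparisons between subgroups are to be made "if the subgroups are of sufficient size for statistical comparison". The same section sets up a modified intention-to-treat analysis of patients who received at least 2 IMiD cycles.

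**The concern.** Eligibility is wider than the field that describes it. A patient in first remission on maintenance, or on first-line treatment 45 days after diagnosis, is eligible but fits neither box. Site staff must then tick the nearest box or leave the field empty. In the first case the relapsed group contains patients who have not relapsed; in the second they drop out of the comparison.

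Two uses of the data are at stake. One is the only disease-status contrast the plan names. The other is the baseline description. The study's stated purpose is to supply event rates for a larger randomized trial, and a reader who wants to carry those rates over needs to know what mix of patients produced them.

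A related gap concerns IMiD exposure. Membership of the modified intention-to-treat set depends on cycles received, and no IMiD dates or cycle counts appear in the CRF pages available.

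**Working it through.** The plan states no figure on this point, so there is nothing to reproduce. The check maps eligible patients to the form and then bounds the size.

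**Step 1. Map each eligible situation to the two boxes.**

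| Situation admitted by the inclusion criteria | Matching box |
|---|---|
| Newly diagnosed, 30 days or less | New diagnosis |
| First-line therapy, more than 30 days from diagnosis | None |
| Relapsed | Recurrent/relapsed |
| Progressive | None named; recurrent/relapsed may be a reasonable choice |
| Maintenance or consolidation, never relapsed | None |
| Maintenance or consolidation after relapse | Recurrent/relapsed |

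**Step 2. See whether other CRF fields repair it.**
- The screening checklist asks only for a myeloma diagnosis, IMiD use, age and consent, not for the treatment setting.
- Date of diagnosis and date of enrollment give elapsed time, so a longer window for new disease could be derived. They do not show whether a patient has relapsed or is on maintenance or consolidation.
- The IMiD field records which drug, with no start date.
- The other-therapies field lists transplantation and drug classes, with no setting or line of therapy.

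**Step 3. Bound the number affected.** Inputs: N = 50 (Sample Size Calculation), and f, the share with no matching box, which the documents do not give. Assume f = 20%, 40% or 60%, with the remaining patients split equally between new and relapsed.

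- Unmatched patients: u = 50 × f.
- If all are ticked as relapsed, the recorded relapsed group is (50 − u)/2 + u = 25 + u/2.
- Share of that group not relapsed: u / (25 + u/2).
- If all are left blank, 50 − u patients remain in the contrast.

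| f | u | Recorded relapsed | Share not relapsed | Left in contrast if blank |
|---|---|---|---|---|
| 20% | 10 | 30 | 10/30 = 33% | 40 |
| 40% | 20 | 35 | 20/35 = 57% | 30 |
| 60% | 30 | 40 | 30/40 = 75% | 20 |

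These are upper bounds for each assumed f: every unmatched patient is handled the same way.

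**Step 4. Ask how much the subgroup could show if perfectly classified.** At the 5% VTE rate in the Sample Size Calculation, 50 × 0.05 = 2.5 events are expected. At the 3% bleeding rate in Hypothesis 1, 50 × 0.03 = 1.5. Take an even 25/25 split with all events in one group. The two-sided Fisher p-value is:
- 3 versus 0: 2 × C(25,3)/C(50,3) = 2 × 2300/19600 = 0.23.
- 2 versus 0: 2 × C(25,2)/C(50,2) = 2 × 300/1225 = 0.49.

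The most extreme split of the expected number of events is therefore far from significance. The subgroup can only describe.

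**Step 5. Check the modified intention-to-treat set.** It needs the number of IMiD cycles per patient. The Study Treatment rows give start and stop dates for the study drug, not for the IMiD. Because patients already on an IMiD may enter, it is also unstated whether cycles before enrollment count.

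**The case against.** **Little depends on this comparison.** The plan calls it potential and makes it conditional on subgroup size, and Step 4 shows that correct classification would not make it informative. This stands, and it makes the point a minor one. It does not justify a field that cannot describe the patients enrolled.

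**The information may exist elsewhere.** The study calendar lists myeloma history and prior and concomitant medications at screening, and outcome data come from the Electronic Health Record. Treatment setting is probably in source. But recovering it would mean unplanned re-abstraction, possibly with outcomes already known. Date of diagnosis settles only the time element.

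**The printed form may not be the final one.** The Study Duration section lists finalizing it as a start-up task, and data go into a web-based eCRF. The form as extracted also appears to have a gap between the study-treatment rows and the venous-event rows. The statement about IMiD dates and cycles is therefore limited to the pages available. The myeloma block looks continuous, so the two-box finding is not affected.

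**Stronger readings that the documents do not support.**
- A reader might infer that all maintenance, consolidation and later first-line patients land in the wrong subgroup. Nothing shown forces a tick, so some may be unclassified instead, and a maintenance patient who has relapsed is recorded correctly.
- A reader might infer that the mixing could reverse a difference between the groups. Nothing in the documents shows this. With 2 to 3 events, instability comes mainly from sparse data, which new fields do not cure.
- A reader might infer that the plan must separate IMiD starters from existing users. It names no such comparison, so a listing of that kind would be an addition, not a correction.

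**Conclusion.** The point holds as a minor defect in data capture. The form has no true option for non-relapsed patients on maintenance or consolidation, or on first-line therapy beyond 30 days, although all are eligible. They would be misclassified as relapsed or left unclassified, so neither the named subgroup nor the baseline case mix can be built correctly from the form.

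The size is unknown. Up to 10 to 30 of 50 patients are affected if 20% to 60% have no matching box; that share is an assumption, and it should not be read as a count of misplaced patients.

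It would be wrong to conclude that the main results are at risk: both primary rates are computed over all patients and do not use this field. The missing IMiD exposure data matter for a different reason, since the 2-cycle analysis set cannot be derived from the CRF pages available.

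**What to change.** 1. Replace the two-box field with the five settings in the Study Inclusion Criteria plus other. If a time window for new disease is kept, name the date it is counted from.
2. Add a sentence to the Statistical Analysis Plan saying how each setting maps to newly diagnosed, recurrent/relapsed or neither, and that the comparison is descriptive.
3. Record IMiD start date and cycles received during the study, and state which cycles count toward the 2-cycle requirement.
4. Optional: list events separately for patients starting an IMiD and those already on one.

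The cost is two or three extra CRF fields and a sentence or two in the analysis plan. The downside is smaller descriptive categories: five settings would average 50/5 = 10 patients each, so they should be reported as counts without testing.

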## **Safety Outcomes**

### **Primary Safety Outcome**

The primary safety outcome is the 6-month rate of major and clinically relevant non-major bleeding in MM patients receiving IMiDs who are prescribed apixaban 2.5 mg orally twice daily for primary prevention of VTE.

Using the ISTH classification, bleeding is defined as major if it is overt and associated with a decrease in the hemoglobin level of 2 g/dL or more, requires the transfusion of 2 or more units of blood, occurs into a critical site, or contributes to death (12).

Using the ISTH classification, clinically relevant nonmajor bleeding is defined as overt bleeding not meeting the criteria for major bleeding but associated with medical intervention, surgical intervention, or interruption of the study drug.

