### **Independent Study Safety Monitor**

A physician with relevant expertise whose primary responsibility is to protect the safety of study subjects and to provide ongoing, critical, and unbiased evaluation of the progress of the study will be appointed as an independent study safety monitor for the duration of the study. The safety monitor will operate in a manner similar to that of a Clinical Events Committee/Data and Safety Monitoring Board.

The safety monitor will:

- Provide independent safety evaluation of events and adjudicate all actual and potential serious adverse events experienced by study subjects during this study;
- Review aggregate safety data including the frequency of adverse safety outcomes, particularly death, symptomatic VTE and major bleeding; and can recommend premature stopping of the study to the Sponsor and Principal Investigator at any time.

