### **Stopping Criteria**

The study will be terminated by the safety monitor, sponsor, and principal investigator if the following stopping criterion is met:

- An excess of morbidity or mortality is observed in patients receiving apixaban.
  - a. When 2 patients receiving apixaban experience an unprovoked intracranial hemorrhage, confirmed by independent adjudication, and did not have a protocol violation such that he/she cannot be considered as representative of the intended patient population.
  - b. When 3 of the subjects receiving apixaban experience an unprovoked major bleed (including fatal hemorrhagic events) and did not have a protocol violation such that he/she cannot be considered as representative of the intended patient population.

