## **Statistical Methods**

### **Sample Size Calculation**

The sample size estimate is completed using the 95% confidence interval (CI) method. We propose a sample size of 50 patients. It generates a half-width of CI less than 10% if the blood clot rate is <15%. Since our study expects an 80% risk reduction in VTE, our estimated VTE rate is about 5%. If based on the 5% VTE incidence rate, the half-width CI will be <6%. Therefore, the precision will be improved with narrower CI, since we expect an incidence much lower than 15%.

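### The CRF's bleed blocks do not match the protocol's bleeding definitions and omit most criteria that set the class, so a non-overt hemoglobin fall can enter the primary safety rate

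*Combined protocol and SAP*

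**What the plan says.** The Primary Safety Outcome section makes the primary safety outcome the 6-month rate of major plus clinically relevant non-major bleeding. On the hemoglobin route, "bleeding is defined as major if it is overt and associated with a decrease in the hemoglobin level of 2 g/dL or more". The other routes to major are transfusion of at least 2 units, bleeding into a critical site, and contribution to death. Critical sites are not listed. A non-major bleed must be overt, must fall short of the major criteria, and must have led to medical or surgical intervention or to interruption of study drug.

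The Case Report Form prints the same location list in its major and non-major blocks. Both lists include "Hematocrit or hemoglobin decrease without clear source" and an intracranial option.

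Under Independent Study Safety Monitor, the monitor is to "adjudicate all actual and potential serious adverse events experienced by study subjects during this study". Under Stopping Criteria, item (a) applies "When 2 patients receiving apixaban experience an unprovoked intracranial hemorrhage" and requires independent adjudication. Item (b) applies at 3 unprovoked major bleeds and does not mention adjudication.

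**The concern.** Outcomes are abstracted from the health record, with no routine study visits (Follow-Up Evaluation) and no control arm. The form is therefore where the primary safety count is made. It offers the abstractor a laboratory change as the site of a bleed, while the definition needs overt bleeding.

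Falls without bleeding are plausible on the plan's own terms. Patients may enter with a hemoglobin as low as 9 (units as printed in the exclusion criteria), and the form records chemotherapy and erythropoiesis-stimulating agents as concurrent therapies. A fall filed as a bleed would raise the primary rate and, if filed as major, the count in stopping item (b). With few events expected among 50 patients, each one matters.

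**Working it through.** **The plan's own figure.** The Sample Size Calculation states "We propose a sample size of 50 patients" and "The sample size estimate is completed using the 95% confidence interval (CI) method". Its precision claims, in percent, are "It generates a half-width of CI less than 10% if the blood clot rate is <15" and "If based on the 5% VTE incidence rate, the half-width CI will be <6". The simple (Wald) half-width is 1.96 × √(p(1−p)/n):

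- p = 0.15, n = 50: 1.96 × √(0.15 × 0.85/50) = 9.90%.
- p = 0.05, n = 50: 1.96 × √(0.05 × 0.95/50) = 6.04%, just above the stated bound.

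The plan's figures are reproduced closely enough to confirm 50 as the denominator. Nothing below changes the sample size.

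**Definition against form.**

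- *Overt bleeding:* needed for the hemoglobin criterion and for all non-major bleeds. Neither block has a field for it.
- *Hemoglobin fall of at least 2 g/dL:* no field for the size of the fall.
- *At least 2 units transfused:* the treatment list has a blood-products box but no number of units.
- *Critical site:* sites can be ticked, but none is marked critical, and the definition lists none.
- *Contribution to death:* the major block asks whether the bleed was fatal, which is close but not the same.
- *Intervention:* partly covered by the treatment list.
- *Interruption of study drug:* absent from both bleed blocks, although the non-bleed drug reaction block records temporary and permanent stops.
- *Provoked or unprovoked:* needed for both stopping items, but has no field.

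A reader of the completed form could not tell whether a ticked class meets the definition.

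**Effect on the primary rate.** The hypothesis of 3% or less (Specific Aims) corresponds to 50 × 0.03 = 1.5 events. One misfiled fall adds 1/50 = 2.0 points. For example, with exact (Clopper-Pearson) 95% intervals:

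- 1/50 = 2.0% (0.05% to 10.7%)
- 2/50 = 4.0% (0.5% to 13.7%)

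The point estimate passes 3%, although both intervals include it.

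**Effect on stopping item (b).** With q the rate at which patients are counted as having a major bleed, P(stop) = 1 − Σ C(50,k) q^k (1−q)^(50−k), k = 0 to 2. Set q = m + f, where m is the true major-bleed rate and f the rate of falls misfiled as major. Both are assumptions. Only m = 0.6% appears in the documents, as the major-bleed rate on apixaban in the cited acute-treatment trial, in a different population and at a different dose.

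| m | f = 0 | f = 2% | f = 4% |
|---|---|---|---|
| 0.6% | 0.3% | 14.1% | 40.6% |
| 1% | 1.4% | 18.9% | 45.9% |
| 2% | 7.8% | 32.3% | 58.4% |
| 3% | 18.9% | 45.9% | 68.9% |

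These figures treat every counted bleed as unprovoked and all 50 patients as followed, with no correction by adjudication. They show sensitivity and do not predict what will happen.

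**Intracranial option.** Moving an intracranial bleed from non-major to major changes the composite by 0 and count (b) by +1. Item (a) counts intracranial hemorrhage whatever its class.

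**The case against.** The location tick follows the class tick: the abstractor first answers whether there was a major or non-major bleed, and a separate yes/no item records the composite. Nothing says that choosing a location overrides the definition. A reader might infer that the form redefines the outcome, but it only permits an error.

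Nor does lack of a clear source mean lack of overt bleeding, since a visible bleed can have no identified origin. That stands, and such bleeds need a place on the form. Even so, the option names a laboratory change rather than a bleed, and Laboratory Test Abnormalities already provides a route for such changes.

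Adjudication is broader than a quick reading suggests. It covers potential as well as actual serious events. The definition of seriousness includes hospitalization and important medical events, and Specific Adverse Event Reporting Guidelines uses a major bleed as its example. Stopping is a decision of the monitor, sponsor and principal investigator, and monthly random data checks are planned. This limits the exposure mainly to non-serious bleeds, but no section says that every bleed is classified against the definition.

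A reader might also infer that the intracranial option in the non-major block can corrupt the primary rate or disable item (a). It cannot, because the composite counts both classes and item (a) ignores class and requires adjudication. The definition does not name intracranial as a critical site either, although the separate two-event rule suggests that the plan regards it as grave.

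Finally, Study Duration places finalizing the form in start-up, so the web-based version may differ from the printed one. If so, that version should be checked for the same mismatch.

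**Conclusion.** The mismatch between form and definition is real and worth correcting, but it does not invalidate the design. Each non-overt hemoglobin fall filed as a bleed would add 2 percentage points to the primary safety rate, assuming 50 patients in the denominator. If filed as major and taken as unprovoked, it would also add 1 to the three-event count in item (b). How often this would happen is unknown. The plan calculates rates and specifies no test against 3%, so the harm is a distorted estimate rather than a false test result.

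The conclusion holds even on the narrow reading that ties overtness only to the hemoglobin criterion of major bleeding, because that is the criterion a hemoglobin fall would invoke. For non-major bleeding, overtness is required outright. The intracranial option affects only the split between major and non-major bleeding and count (b).

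**What to change.** 1. Take the hemoglobin option out of both outcome blocks and record such falls as laboratory events under Laboratory Test Abnormalities. Keep an entry for other or unknown source, for overt bleeds whose origin is not found.
2. For each bleed, add fields for overt yes/no, hemoglobin change, units transfused, critical site, contribution to death, medical or surgical intervention, interruption of study drug, and provoked/unprovoked.
3. List the critical sites in the Primary Safety Outcome section, then reconcile the intracranial option in the non-major block with that list.
4. Derive the class from these fields instead of from a tick.

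The cost is a CRF edit, a short addition to the definition, and a little more abstraction and programming per bleed. The sample size and planned analyses do not change.
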